Adherence to the non-surgical intervention is assessed by the percentage of patients being referred for non-surgical treatment, and the actual number of patients with a minimum of 1 record, in the REDCap database, of receiving non-surgical intervention after the initial clinical examination: Adherence% = (Number of patients with a record of receiving non-surgical intervention/number of patients referred for non-surgical intervention) x 100. Treatment adherence will be presented with descriptive statistics (N, %) by randomisation group.

Patient's crossing over to receive surgery from the non-surgical intervention group within one year from allocation and patients from the surgical group without a record in the REDCap database of surgery performed will be considered a major protocol deviation. Furthermore, patients in both groups withdrawing from the trial between baseline and one year follow-up will be considered as a major protocol deviation. Minor deviations are not completing all follow-up measurement. The number (percentage) of patients with respectively major and minor protocol deviations will be summarised by treatment group. No formal statistical testing will be conducted.

Analysis populations

The primary analysis will be performed on the Intention-to-treat (ITT) population, including all eligible patients according to the treatment they were initially allocated (initial clinical decision at first medical examination) to receive. A sensitivity analysis will be considered based on the per-protocol population, if >5% of the total number of patients in one treatment group are major protocol violators. The per-protocol analysis set will include: 1) patients who in the surgical group were allocated (initial clinical decision at first medical examination) to receive surgery, and have a record of the surgery was performed in the REDCap database, including date and type of surgery performed, 2) patient who in the non-surgical group were allocated (initial clinical decision at first medical examination) to receive non-surgical treatment and a minimum of 1 record within 4 months, in the REDCap database, of receiving non-surgical intervention after the initial clinical examination as well as no record of surgery performed.

Trial population

Screening data

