The primary analyses will be based on the Intention to Treat (ITT) population. Categorical endpoints (e.g., the proportion achieving PASS/Quick-DASH MIC after 1 year) will be analysed using logistic regression, with treatment group and stratification factors as covariates, based on the IPW data provided initially. The primary estimand will be the odds ratio (OR) with 95% confidence intervals (CIs) derived from the fully adjusted logistic regression model. The main analysis will use inverse probability weighting, with further adjustment for stratification variables. The OR will represent the treatment effect, with CIs providing the range within which the true treatment effect is expected to lie with 95% certainty. A p-value will be reported to assess the statistical significance of the treatment effect, testing the null hypothesis of no difference between groups. An OR >1 indicates higher odds of achieving the PASS/Quick-DASH MIC outcome with surgical treatment, while an OR <1 indicates lower odds. For secondary objectives, categorical outcomes will be analysed using the same approach as the primary endpoints, while continuous outcomes will be analysed as change from baseline using repeated-measures mixed-effects linear models. Patient identification number will be included as a random effect. Fixed effect factors will include baseline score, treatment group (Shoulder Surgery vs Nonoperative Treatment), time point (baseline, 3, 6, and 12 months), stabilised inverse probability of treatment weighting (sIPTW), and treatment-by-time interactions.

Sensitivity analysis will be performed with the purpose to test the robustness of the primary analyses, based on the per-protocol population, if $>5\%$ of the total number of patients in one treatment group are major protocol violators. The per-protocol analysis set will include: 1) patients who in the surgical group were 'allocated (initial clinical decision at first medical examination) to receive surgery, and have a record of the surgery was performed in the REDCap database, including date and type of surgery performed, 2) patient who in the non-surgical group were allocated (initial clinical decision at first medical examination) to receive non-surgical treatment and a minimum of 1 record, in the REDCap database, of receiving non-surgical intervention after the initial clinical examination as well as no record of surgery performed.

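### The per-protocol set does not match the major-deviation rule that triggers it: late surgery in the non-surgical arm and withdrawals are handled differently in the two

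*SAP*

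**What the plan says.** Under Adherence and protocol deviations, the SAP names three major deviations:

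- non-surgical patients "crossing over to receive surgery from the non-surgical intervention group within one year from allocation";
- "patients from the surgical group without a record in the REDCap database of surgery performed will be considered a major protocol deviation", with no time window;
- "patients in both groups withdrawing from the trial between baseline and one year follow-up will be considered as a major protocol deviation".

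Under Analysis populations, a per-protocol analysis comes into play "if >5% of the total number of patients in one treatment group are major protocol violators". Surgical-arm patients enter the set if they "have a record of the surgery was performed in the REDCap database, including date and type of surgery performed". Non-surgical patients need "a minimum of 1 record within 4 months, in the REDCap database, of receiving non-surgical intervention" and, in addition, "as well as no record of surgery performed".

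Analysis methods repeats the definition. The surgical criterion is the same. For the non-surgical arm it asks for at least one record of "receiving non-surgical intervention after the initial clinical examination as well as no record of surgery performed", this time without the 4-month window. Neither version mentions withdrawal.

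The primary and co-primary endpoints are fixed at 1 year after allocation. Under Missing data, categorical endpoints missing at 1 year are set to non-response.

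**The concern.** A per-protocol set should leave out the patients whom the plan calls major deviators. Here the rule that triggers the analysis and the rule that builds the set describe different people, and the differences are not neutral.

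- **Late surgery in the non-surgical arm.** A patient operated on after the 1-year assessment complied throughout the period in which the outcome arose. Removing that patient selects on something that happened after the outcome. If late operations go mainly to patients still doing badly at one year, which is plausible but not documented, their removal raises the non-surgical response rate and favours non-surgical care. The time available for such a record also depends on the enrolment date.
- **Withdrawals.** They can set off the analysis and then remain in it. If the non-responder rule is carried over to this set, they count as treatment failures in an analysis meant to describe patients who followed the plan.
- **Late surgery in the surgical arm.** A patient not yet operated on when PASS was measured could count as adherent to surgery.

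This is the only sensitivity analysis that the SAP names for the primary result, and two analysts could build different sets from the same text.

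**Working it through.** **1. The texts side by side**

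| Patient | Major deviation? | In the per-protocol set? |
|---|---|---|
| Non-surgical, operated on within 1 year | Yes | No |
| Non-surgical, operated on after 1 year | No | No: any surgery record excludes |
| Surgical, no surgery record | Yes | No |
| Surgical, first operated on after 1 year | No: rule is untimed | Yes: criterion is untimed |
| Either arm, withdrew before 1 year, treatment-record criteria met, data usable | Yes | Yes |
| Non-surgical, first non-surgical record after month 4 | Not listed | No under Analysis populations, yes under Analysis methods (if no surgery record) |

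Rows 2 and 5 contradict the deviation rule. Row 4 does not, but lets a post-outcome event decide membership. Row 6 is a conflict between the two definitions of the set.

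**2. Group sizes, from Sample size and power considerations**

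N = 992 at 1:15 gives 992/16 = 62 surgical and 930 non-surgical patients. The stated power reproduces:

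- pooled rate = (62 × 0.80 + 930 × 0.60)/992 = 0.6125
- null SE = √[0.6125 × 0.3875 × (1/62 + 1/930)] = 0.0639
- alternative SE = √[0.80 × 0.20/62 + 0.60 × 0.40/930] = 0.0533
- z = (0.20 − 1.96 × 0.0639)/0.0533 = 1.40, so power is 0.92, as stated.

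This figure is not in dispute; it only supplies the group sizes and rates used below.

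**3. The trigger**

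0.05 × 62 = 3.1 and 0.05 × 930 = 46.5. More than 5% therefore means at least 4 surgical or 47 non-surgical patients. Withdrawals alone could reach that number and start an analysis that removes none of them.

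**4. Time available for late records**

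Enrolment began in January 2021 and last follow-up was in January 2025 (Trial design). If surgery records run to January 2025 (assumption), the first patients have about 3 years after their 1-year endpoint (January 2022 to January 2025) and the last have none.

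**5. Illustration: late surgery in the non-surgical arm**

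The SAP gives neither input. Assume that a share c = 5% of the arm (0.05 × 930 ≈ 47 patients) is operated on after one year, with 1-year PASS q among them. After dropping them the arm's rate is (0.60 − c × q)/(1 − c):

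- q = 10%: (0.60 − 0.005)/0.95 = 0.626
- q = 35%: (0.60 − 0.0175)/0.95 = 0.613

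The design OR is (0.80/0.20)/(0.60/0.40) = 2.67. It becomes 4/(0.626/0.374) = 2.39 and 4/(0.613/0.387) = 2.52. With no true difference (60% in both arms), the OR becomes 1.5/(0.626/0.374) = 0.90 and 1.5/(0.613/0.387) = 0.95.

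**6. Illustration: withdrawals kept as non-responders**

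Assume an equal withdrawal share w in both arms, unrelated to outcome, with every withdrawal meeting the record criteria. At w = 10% the rates become 0.80 × 0.90 = 0.72 and 0.60 × 0.90 = 0.54, so OR = (0.72/0.28)/(0.54/0.46) = 2.19. At w = 5% and 20% the OR is 2.39 and 1.93. If withdrawals are excluded it stays at 2.67.

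Steps 5 and 6 are unweighted; the planned model uses stabilised weights and stratification factors.

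**The case against.** Several limits on this point are fair and stand.

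- A reader might infer that the surgical-arm criterion breaks a one-year rule. It does not. The one-year limit attaches only to crossover from the non-surgical group; the surgical-arm deviation is itself untimed and agrees with the set. A one-year limit there would be new.
- A reader might infer that patients will in fact be classified by events after the endpoint. The SAP does not show this. It schedules no assessment beyond 1 year and does not say whether later operations are entered in REDCap. If recording stops at one year, the timing problem has no effect in either arm. The withdrawal mismatch remains.
- Not every withdrawal stays in the set. Withdrawal/Follow-up has a category in which consent for data already collected is also withdrawn, and patients who leave before any treatment record exists fail the inclusion criteria.
- Counting the remaining withdrawals as non-responders is an inference. The Missing data section states its rule for categorical endpoints in general, and the Table 2 footnote ties it to ITT analyses; neither mentions the per-protocol set. With equal withdrawal in both arms and no true difference, the OR would stay at 1.
- The illustrated late-surgery effect is small beside sampling error. At 60% in both arms the unweighted SE of the log OR is √[1/(62 × 0.24) + 1/(930 × 0.24)] = 0.27. An OR of 0.95 (log −0.055) is a shift of about 0.2 SE, and 0.90 (log −0.11) about 0.4 SE. An assumed 5% is about 47 patients, against a whole surgical arm of 62.

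None of this removes the mismatch in the text: the crossover rule has a time limit and the set criterion does not, and withdrawal is a deviation that the set ignores.

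**Conclusion.** The point holds as an inconsistency between the major-deviation rule and both definitions of the per-protocol set. It lies in the untimed surgery exclusion for the non-surgical arm and in the treatment of withdrawals. The 4-month window is a further conflict between the two definitions. In the surgical arm the fault is only that an operation after the 1-year outcome would qualify.

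The size cannot be derived from the SAP. The movement to about 61–63% in non-surgical PASS depends wholly on the assumed 5% and the assumed 10–35%; the withdrawal figures depend on assumed shares and on non-responder imputation being applied to this set. They show direction and order of magnitude, not an expected bias.

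It would be wrong to read this as a threat to the main result. The primary analysis is by ITT and is untouched, and the per-protocol analysis runs only if the 5% trigger is met. Severity is low, but the definitions should be settled before the data are extracted.

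**What to change.** Make these changes under Adherence and protocol deviations, Analysis populations and Analysis methods, so that all three agree:

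1. **Non-surgical arm:** exclude from the set only patients with surgery recorded between allocation and the 1-year assessment, in line with the existing crossover rule.
2. **Surgical arm:** count a surgery record as adherence only if it is dated on or before the 1-year assessment. This limit is new, so add it to the surgical-arm deviation rule as well. It classifies records for analysis and says nothing about when surgery should take place.
3. **Withdrawals:** exclude patients who withdraw before one year from the per-protocol set, so that the set matches the trigger.
4. **Non-surgical record:** reconcile the 4-month window, which appears under Analysis populations but not under Analysis methods. State it in both places or in neither.

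The cost is SAP wording only. The set already requires the date of surgery in REDCap, so no new data are needed, and the ITT analysis and sample size do not change.

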In this pragmatic emulation of a stratified, randomised, open-label, superiority trial, adults referred to secondary care with various shoulder diagnoses and medical imagine verified pathology were initially allocated into either Surgery group, or the Non-Surgical Treatment group with an expected allocation ratio of 1:15. The primary endpoint in the intention-to-treat population was PASS assessed one year from allocation of treatment. Secondary endpoints was assessed also at 3 and 6 months after allocation of treatment. We will analyse observational data from the prognostic Vejle Hospital Shoulder Cohort (VHS Cohort), initiated to evaluate prognostic factors for consistent pain 1 year after diagnosis, using a “causal inference framework”, in an attempt to emulate a randomised target trial, stratified per diagnostic group defined as 1) Degenerative; 2) Traumatic injury; 3) Non-traumatic instability/luxation; 4) Non-specific pain, based upon ICD-10 diagnosis and traumatic/non-traumatic anamnesis (Illustration 1), that would answer the question whether more patients referred for surgery based on a surgeon’s clinical evaluation will reach a satisfactory outcome, when compared to patients not referred for surgery. Thus, causal inference from these observational data needs to be evaluated with respect to how well they emulate a particular target trial that is not feasible/ethical to perform.

[figure not shown]

Illustration 1: Diagnostic grouping based on ICD-10 diagnoses.

The statistical analysis plan (SAP) is reported in accordance with the “Guidelines for the Content of Statistical Analysis Plans in Clinical Trials”.²⁴ Reporting of the trial will follow the “Consolidated Standards of Reporting Trials” (CONSORT).^{25 26}

The trial was registered at Clinicaltrials.gov (NCT04686435) in 12/2020. First patient was enrolled in January 2021. Last patient last follow-up was January 2025. The trial has been evaluated and approved by The Regional Committees on Health Research Ethics for Southern Denmark (Project.ID: S-20202000-16) and the Danish Data Protection Agency (journal no: 20/12316).

Group allocation

Allocation to surgery or non-surgical treatment is based on the clinician’s initial overall judgment, taking into account patient history, clinical examination, imaging findings, patient expectations, relevant clinical guidelines and shared decision making. This real-world allocation process was analytically emulated to reflect a trial-like comparison.

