Sample size and power considerations

The sample size calculation applies jointly to both primary efficacy objectives. A power analysis for comparing two proportions using Pearson’s chi-square test indicated that, with a 1:15 allocation ratio between groups, a total sample size of 992 would provide 92% power to detect a 20 percentage point absolute difference (0.80 vs. 0.60) at a two-sided significance level of 5% ($\alpha = 0.05$). The calculation employed a normal approximation to the binomial distribution under the null hypothesis of no difference in proportions. For practical and operational considerations, the sample size was rounded up to 1000 participants to ensure sufficient power and account for potential deviations.

Framework

Both primary and secondary outcomes are analysed within a superiority framework; surgical interventions are favourable compared to non-surgical interventions.

Statistical interim analysis and stopping guidance

No statistical interim analysis is planned on the primary endpoint.

Timing of final analysis

Data extraction and analysis for the between-group comparison (Surgical vs. Non-Surgical) for the primary endpoint (1 year follow-up) is planned to be performed after making this SAP public available. The main publication of the trial will be prepared when these data have been received and cleaned (anticipated by September 2025).

Timing of outcome assessments

The overview of trial procedures and time-point of each outcome assessment is presented in the **Illustration 2** “Timeline for recruitment and follow-up” and **Box 1** “Outcomes and Covariates – Timepoint of assessment”. The Treatment allocation date (Surgical or Non-surgical) is used to calculate 3 months, 6 months and 1 year follow-up time points.

[figure not shown]

Illustration 2: Timeline for recruitment and follow-up. -t₂: 2-4 days prior to medical examination; -t₁=Day of medical examination; t₀=Allocation; t₁= 3 months; t₂= 6 months; t₃= 1 year.

STATISTICAL PRINCIPLES

Confidence intervals and p-values

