Subgroup analyses will be performed if imbalance is seen in the applied stratification sequence, only including diagnostic subgroups with balanced patient distributions between surgical treated patients and non-surgical treated patients.

Missing data

Missing data are ignorable only when they are missing completely at random (MCAR), meaning no systematic differences exist between missing and observed values. More commonly, data are assumed to be missing at random (MAR), where any systematic

differences can be explained by observed variables.²⁷ Under the MAR assumption, repeated measures mixed-effects models or multiple imputation is recommended as it yields valid standard errors, P values, and confidence intervals.⁴⁶ For categorical efficacy endpoints, missing data at 1 year from baseline will be addressed through non-responder imputation, which is supposedly representing a conservative approach. For continuous efficacy endpoints repeated measures mixed effects models will handle missing data; missing data will be handled indirectly with the use of the mixed-effects linear-models approach with an assumption that data were missing at random, in accordance with the working assumption underlying these models.⁴⁷

Additional analyses

No additional analyses are planned.

Harms

No data on harm was collected.

Statistical software

All statistical analyses will be conducted using SAS (SAS Institute Inc) and R (R Foundation for Statistical Computing). SAS will be used primarily for data management and modeling, while R will be applied for supplementary analyses, data visualisation, and reproducibility checks.

REFERENCES:

1. Lucas J, van Doorn P, Hegedus E, et al. A systematic review of the global prevalence and incidence of shoulder pain. *BMC Musculoskelet Disord* 2022;23(1):1073. doi: 10.1186/s12891-022-05973-8 [published Online First: 2022/12/09]

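### Which diagnostic subgroups get analysed depends on an undefined balance judged from the data, and no treatment-by-diagnosis interaction is planned

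*SAP*

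**What the plan says.** One sentence at the end of Analysis methods governs all subgroup work. Its trigger is: "Subgroup analyses will be performed if imbalance is seen in the applied stratification sequence". Its inclusion rule is: "only including diagnostic subgroups with balanced patient distributions between surgical treated patients and non-surgical treated patients". No metric, cut-off, endpoint or model is given for these analyses.

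The related text is as follows.

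- Trial design names the candidate groups in advance: "stratified per diagnostic group defined as 1) Degenerative; 2) Traumatic injury; 3) Non-traumatic instability/luxation; 4) Non-specific pain". It describes the two arms "with an expected allocation ratio of 1:15". This is an overall figure, and no ratio per diagnostic group appears.
- Analysis populations defines the primary population as "including all eligible patients according to the treatment they were initially allocated". The propensity-score notation in Analysis methods likewise sets T = 1 for initial allocation to surgery.
- Analysis methods fits the binary endpoints by weighted logistic regression, with treatment and the stratification factors as covariates. The only interaction named is treatment by time, for the continuous outcomes.
- Baseline patient characteristics uses standardised differences to judge imbalance, without a threshold. This is the only balance metric in the SAP, and it is not tied to the subgroup rule.
- Additional analyses plans nothing further.

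**The concern.** The emulated trial pools four clinically different groups under a single odds ratio. A reader will want to know whether that ratio describes degenerative disease, traumatic injury, instability and non-specific pain alike. The subgroup rule is the only place where the SAP could answer this, and it leaves the choice of groups open. Two analysts could apply the sentence in good faith and report different sets.

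The rule also works against its purpose. Groups judged unbalanced drop out of subgroup reporting but stay in the pooled estimate, although these are the groups where overlap between the arms most needs scrutiny. Showing a selected group or two without an interaction test invites over-reading. Finally, the words for the two arms in this sentence do not match the allocation-based definition used in the main analysis.

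**Working it through.** **1. The plan's own power figure.** Inputs from Sample size and power considerations: N = 992 at 1:15, so 992/16 = 62 surgical and 930 non-surgical; proportions 0.80 and 0.60; two-sided alpha 0.05. Pooled variance is used under the null and unpooled under the alternative.

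- Pooled proportion: (0.80 + 15 × 0.60)/16 = 0.6125.
- Null SE: √[0.6125 × 0.3875 × (1/62 + 1/930)] = 0.0639.
- Alternative SE: √(0.16/62 + 0.24/930) = 0.0533.
- Power: Φ[(0.20 − 1.96 × 0.0639)/0.0533] = Φ(1.40) = 0.920.

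The stated 92% reproduces. At the rounded N of 1000 (62.5 vs 937.5) power is 0.922.

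**2. What the rule's logic yields.** If the trigger and the inclusion rule refer to the same property of a stratum (an assumption), then:

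- all four balanced: the trigger is not met and nothing is analysed;
- some unbalanced: only the others are analysed, so three at most;
- all unbalanced: none qualifies.

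On that reading all four groups are never reported together. If the two terms mean different things, the SAP does not say what either means.

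**3. If balanced means similar arm sizes.** Suppose a stratum follows the overall ratio, with surgical share 1/16 (assumption). The binomial chance of reaching a given surgical share, for illustrative cut-offs, is:

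| Stratum size | at least 20% surgical | at least 40% surgical |
|---|---|---|
| 20 | 0.033 | 1.5e-5 |
| 50 | 9.2e-4 | 6.2e-12 |
| 100 | 3.4e-6 | 2.2e-22 |

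Strata need not follow 1:15, however. With about 62.5 surgical patients in all, strata with equal arms could together hold up to 62.5 + 62.5 = 125 patients, or 12.5% of 1000, if every surgical patient fell in them.

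**4. Other readings.** If balanced means covariate balance, or a surgical share close to the overall one, the 1:15 ratio does not prevent any group from qualifying. The answer therefore turns on a definition that the SAP does not give.

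**5. Precision within strata, under any rule.** The formula of step 1 is applied to a stratum holding a given share of 1000 patients at 1:15. The shares are assumptions, because the SAP gives none.

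| Share | Surgical vs non-surgical | Power, 0.80 vs 0.60 |
|---|---|---|
| 10% | 6.25 vs 93.75 | 0.12 |
| 25% | 15.6 vs 234.4 | 0.32 |
| 50% | 31.25 vs 468.75 | 0.62 |
| 70% | 43.75 vs 656.25 | 0.79 |

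For an even split of 992 (15.5 vs 232.5) with 0.60 in both arms, the SE of the log odds ratio is √[1/(15.5 × 0.24) + 1/(232.5 × 0.24)] = 0.535. An observed odds ratio of 1.0 then has a 95% CI of exp(±1.96 × 0.535), or 0.35 to 2.86. These figures are unweighted, so any loss from weighting comes on top.

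**The case against.** Four stronger readings are tempting, and the SAP supports none of them.

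- **That a 1:15 design cannot produce a qualifying subgroup.** This assumes that balance means equal numbers and that every stratum follows 1:15. The SAP says neither, and elsewhere it speaks of balance in terms of baseline confounders.
- **That subgroups are chosen by treatment actually received.** The wording can be read so, but the SAP also uses treated and treatment loosely for the allocated groups. The propensity-score text calls those allocated to surgery the treated group, and the primary odds ratio is described as an effect of surgical treatment. Where treatment received is meant, a REDCap record is cited, and this sentence cites none. It is an ambiguity to remove, not a proven switch to as-treated groups.
- **That subgroups are picked on outcome.** The candidates are fixed in advance, and the stated criterion is how patients are distributed by treatment. With no cut-off and no stated blinding to outcomes for that judgement, outcome-driven choice is not excluded, but it is not planned.
- **That low subgroup power measures the harm of this rule.** It comes from the small surgical arm and would affect the replacement just as much.

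It is also fair to say that leaving out strata with too little overlap is defensible in a weighted analysis. No subgroup objective is stated, and subgroup results are outside the hierarchical testing sequence that limits inferential claims. All of this stands and limits the point's weight. It does not supply the missing definition or test the common odds ratio.

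**Conclusion.** The point holds as a recommended improvement. The subgroup trigger and inclusion rule depend on observed distributions judged by undefined terms, so the set of reported diagnostic groups is not fixed in advance. The primary model assumes one odds ratio across four strata, and no planned analysis examines that. Only on the similar-arm-size reading, and only for strata near 1:15, would groups almost never qualify. The wording for the arms needs to be aligned with initial allocation.

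The primary and key secondary estimates do not change. What is at stake is how far the pooled odds ratio can be interpreted by diagnosis, and whether subgroup reporting is selective. The within-stratum power range rests on assumed stratum shares with 1:15 in each, and it describes general imprecision.

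**What to change.** Replace the subgroup sentence with:

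> In the ITT population (by initial allocation), a treatment-by-diagnostic-group interaction will be added to the weighted primary model. Odds ratios with 95% CIs and numbers per arm will be shown for all four groups as exploratory results. Groups with too few surgical patients to estimate will be stated as such.

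This removes the need for a balance metric or cut-off, settles how the arms are defined, and ends selection among the groups. It costs a wording change and one extra model, and should be made before the data are analysed. The downside is that group-specific intervals will be wide and the interaction test weak, so a non-significant interaction must not be read as evidence that the effect is the same in every group.
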